Feasibility of ambulatory pleurodesis
Protocol V2
IRAS: 330188
CI: [name]
26/06/2023

PROTOCOL

Study Title:	Feasibility of ambulatory pleurodesis
Chief Investigator:	[name]
Sponsor:	TVRA
Funder:	TVRA

Feasibility of ambulatory pleurodesis
Protocol V2
IRAS: 330188
CI: [name]
26/06/2023

TABLE OF CONTENTS:

- 1. Study Summary**
- 2. Trial Background**
- 3. Objectives and Study End Points**
 - Primary Objective
 - Secondary Objectives
 - Primary Outcome Measure
 - Secondary Outcome Measures
- 4. Overview of study pathway**
- 5. Selection of Patients**
 - Inclusion Criteria
 - Exclusion Criteria
 - Screening and Informed Consent
 - Screening Logs
- 6. Study Procedures**
- 7. Data Collection**
 - Case Report Form
- 8. Data Management & Confidentiality**
 - Confidentiality
 - Missing Data and Data Queries
- 9. Safety Reporting**
 - Definitions of Adverse Events
 - Reporting Procedures
- 10. Trial Management & Sponsor Oversight**
 - Trial Management Group
 - Sponsorship and Monitoring Arrangements
- 11. Withdrawal of Patients from Trial**
 - Handling withdrawal requests
 - Use of data following withdrawal
- 12. Trial Funding**
- 13. Publication and Dissemination Plans**
- 14. References & Bibliography**

Feasibility of ambulatory pleurodesis
 Protocol V2
 IRAS: 330188
 CI: [name]
 26/06/2023

1. STUDY SUMMARY:

Overall Aim:	Is the study protocol deliverable?
Primary Objective:	
 Can patients with malignant pleural effusions undergo chest drainage and talc. Pleurodesis on an ambulatory basis
Secondary Objective	
 What are the patient perspectives of this protocol?
Target Accrual:	10 patients
Inclusion & Exclusion Criteria:	
Inclusion
 
 Malignant pleural effusion Life expectancy >30 days WHO PS 1-2 (3 if due to exertional dyspnoea) 
Exclusion
 
 Previous failed pleurodesis Known non-expansile lung

Feasibility of ambulatory pleurodesis
Protocol V2
IRAS: 330188
CI: [name]
26/06/2023

	
 • Pregnancy • Age <18
Data Collection Summary:	•
Anticipated Duration of Recruitment	12 months
Duration of Patient Follow-up	30 days
Definition of End of Trial	Drain removal and completion of d+30 questionnaire

2. BACKGROUND

AIMS AND OUTCOMES:

Patients with malignant pleural disease often experience a significant symptom burden and a short life expectancy. The cornerstone of their treatment is relieving breathlessness by draining fluid from around the lungs and attempting to prevent further fluid build up. Inpatient chest drainage and talc pleurodesis remains the most successful method of stopping the fluid build up but this often requires an average hospital stay of four days. This can be an inappropriate length of time for this patient group. Our study would investigate whether this treatment could be provided on an ambulatory basis and facilitate a greater quality of life.

We would assess deliverability of the trial protocol and collect patient feedback to see if our patients consider it an acceptable and worthwhile intervention.

3. Primary Objective

Can patients with malignant pleural effusions undergo chest drainage and talc. Pleurodesis on an ambulatory basis

Secondary Objective

What are the patient perspectives of this protocol?

Primary Outcome Measure:

Success delivery of study protocol

Secondary Outcome Measure:

Patient questionnaire

4. OVERVIEW OF STUDY PATHWAY:

Eligible patients will be offered enrolment in the trial along with standard of care options.

If patients agree to participate in the trial they would be consented for chest drain, talc pleurodesis on an ambulatory pathway.

On day 1:

- A standard chest drain would be inserted in the morning and large volume fluid removal would commence using an underwater seal bottle- as per standard care. We would remove 1000mls of fluid (stopping earlier if not tolerated) and then clamp the drain for one hour.
- We would then open the drain again and drain up to 500mls before again clamping for one hour.
- We would repeat this process as frequently as possible until the end of the working day.
- The drain would then be connected to an ambulatory bag and left in the open position.
- The patient would then be sent home to return on day 2.

On day 2:

- The drain would be flushed, aspirated and the output assessed.
- If there is still fluid output we would drain up to 500mls and close the drain for an hour and repeat.
- If there is no further output we would arrange a chest x ray to ensure the effusion has resolved and the lung has fully inflated.
- If it has we would proceed to talc slurry instillation (with 20mls 1% lidocaine as per standard practice) and clamp the drain for 2 hours.
- After this we would open the drain again and drain up to 500mls and close the drain for an hour.
- We would repeat this as required and again the patient would return home with an ambulatory bag left open.
- If the effusion has resolved but the lung has not fully expanded due to underlying disease then we would simply remove the chest drain as pleurodesis will not be possible.

On day 3:

- The drain would be flushed, aspirated and the output assessed.
- If there is still fluid output we would drain up to 500mls and close the drain for an hour and repeat.
- If there is no further output we would arrange a chest x ray to ensure the effusion has resolved.

Feasibility of ambulatory pleurodesis
Protocol V2
IRAS: 330188
CI: [name]
26/06/2023

- We would then remove the drain and repeat the x-ray to confirm there have been no complications.
- We would then consider the intervention complete and revert to standard care

If there was still significant fluid output we would repeatedly drain 500ml volumes of fluid and clamp the drain for an hour after each 500ml until dry.

We would ask patients to complete a very brief questionnaire (visual analogue scale) on breathlessness and chest pain on day 1 - before intervention, 1 hour post drain insertion, at the end of the day and on day 2 and 3 on first encounter and at the end of the day. We would also repeat the questionnaire on day 30 along with their satisfaction with the protocol.

DAY 1	DAY 2	DAY 3	DAY 4
Seldinger 16Fg drain inserted	Assess output - aspirate and flush drain. Proceed to D3 if no out put.	Assess output - aspirate and flush drain. Repeat Day 2 protocol if required	Assess output: if >240mls / 24 hours repeat Day 2 protocol
Thoracocentesis – up to 1000mls or patient tolerance	Thoracocentesis – up to 500mls or patient tolerance	CXR to confirm >75% pleural apposition	Seldinger drain removed
Clamp for 1 hour	Clamp for 1 hour	Instil 4g steritalic with 3mg/kg Lidocaine and 50ml 0.9% NaCL flush	CXR to confirm >75% pleural apposition
Thoracocentesis – up to 500mls or patient tolerance	Thoracocentesis – up to 500mls or patient tolerance	Clamp for 2 hour	
Repeat as able	Repeat as able	Connect to ambulatory bag and leave 'open'	
Connect to ambulatory bag and leave 'open'	Connect to ambulatory bag and leave 'open'		

5. SELECTION OF PATIENTS:

Inclusion criteria:

- Malignant pleural effusion
- Life expectancy >30 days
- WHO PS 0-2 (3 if due to exertional dyspnoea)

Patient exclusion criteria:

- Previous failed pleurodesis
- Known non-expansile lung

Feasibility of ambulatory pleurodesis
Protocol V2
IRAS: 330188
CI: [name]
26/06/2023

- Pregnancy
- Age <18

Screening and Informed Consent:

Potential candidates will be referred to the respiratory (pleural) team for standard care. Eligible candidates will be offered trial enrolment as an additional option by the PI/CI or delegates and undergo written consent.

SAMPLE SIZE

Number of participants and records

10 patients

Statistical analysis plan

Thematic analysis of patient feedback

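### Section 4 describes the intervention twice, with conflicting rules for giving talc, removing the drain and dosing lidocaine, and does not say which version governs

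*Protocol*

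**What the plan says.** Section 4 (Overview of study pathway) gives the intervention first as a narrative by day and then as a table with columns for Days 1 to 4.

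- **Talc, narrative (Day 2).** Once the drain yields nothing more, the team would "arrange a chest x ray to ensure the effusion has resolved and the lung has fully inflated". If so, talc follows. The alternative is explicit: "If the effusion has resolved but the lung has not fully expanded due to underlying disease then we would simply remove the chest drain", the reason given being that pleurodesis cannot then work.
- **Talc, table (Day 3 column).** The check before talc is "CXR to confirm >75% pleural apposition".
- **Drain removal, narrative (Day 3).** "The drain would be flushed, aspirated and the output assessed". Then: "If there is no further output we would arrange a chest x ray to ensure the effusion has resolved". The drain is taken out after that, and a further x-ray looks for complications. A closing paragraph adds: "If there was still significant fluid output we would repeatedly drain 500ml volumes of fluid", with clamping between volumes, until the patient is dry.
- **Drain removal, table (Day 4 column).** "Assess output: if >240mls / 24 hours repeat Day 2 protocol". The next row removes the drain, and the row after that is an x-ray for more than 75% apposition.
- **Lidocaine with talc.** The narrative specifies 20 ml of 1% solution; the table specifies 3 mg/kg.

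Section 5 excludes "Known non-expansile lung". Section 3 makes successful delivery of the study protocol the primary outcome, and Section 8 requires deviations to be reported to the sponsor and Chief Investigator. Nothing in the document ranks the narrative above the table or the reverse.

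**The concern.** In most trials a mismatch between a narrative and a summary table is an editing matter. Here the primary outcome is whether the protocol was delivered, so the pathway text is also the measuring standard. Where the two versions instruct different actions, a clinician who follows one departs from the other. The same care could then be scored as delivery or reported as a deviation, depending on which half of Section 4 the assessor reads. The talc criterion matters most, because it decides who receives the pleurodesis that the primary objective asks about.

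**Working it through.** The protocol states no figure that can be reproduced for this point. The check is a rule-by-rule comparison, with one piece of arithmetic for lidocaine. Each table column is read from top to bottom as a sequence, which the order of insertion, drainage and clamping in the earlier columns supports.

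**1. Who gets talc.** Take a patient who is dry, with the effusion resolved and 80% apposition on x-ray because of underlying disease.
- Narrative: the lung is not fully expanded, so the drain is removed and no talc is given.
- Table: 80% exceeds 75%, so talc is given.

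The actions are opposite. The conflict covers apposition above 75% but short of full expansion. The exclusion in Section 5 does not remove these patients, because it covers only non-expansile lung that is already known. The narrative itself plans for incomplete expansion discovered after drainage.

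**2. When the drain comes out after talc.**
- *Output above 0 and up to 240 ml/24 h, for example 200 ml.* Table: 200 is not above 240, so the drain is removed. Narrative: there is still output, so drainage continues in steps of up to 500 ml until dry, and removal follows.
- *Output of 240 ml/24 h or less, effusion still present on x-ray.* Table: the drain is removed, and the x-ray is listed afterwards. Narrative: the x-ray comes before removal and is there to ensure resolution, so removal is not yet cleared.

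The x-ray after removal also has different purposes: complications in the narrative, apposition in the table.

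**3. Lidocaine.**
- Narrative: 1% = 10 mg/ml, so 20 ml × 10 mg/ml = 200 mg, whatever the weight.
- Table: 3 mg/kg × weight.
- Equal when 3 × weight = 200, so weight = 200 / 3 = 66.7 kg.
- The protocol gives no body weights. Assuming 50 to 90 kg, the table's dose runs from 3 × 50 = 150 mg to 3 × 90 = 270 mg, against 200 mg fixed. Over the same range the fixed dose is 200 / 50 = 4.0 mg/kg to 200 / 90 = 2.2 mg/kg.

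**4. Weight of one patient.** If delivery is reported as a proportion of the 10 planned patients, each patient classified differently moves it by 1/10 = 10 percentage points. The document gives no basis for estimating how many patients fall in the conflicting ranges.

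**The case against.** The strongest defence is that the section is headed as an overview and that the table is its operational form, since it carries the drain size, talc dose and numerical thresholds. On that view, more than 75% apposition is simply how a fully inflated lung is judged on x-ray, and more than 240 ml/24 h is what significant output means. Both are plausible intentions, but the text states neither. The first sits badly with the narrative's statement that pleurodesis is not possible without full expansion. The second does not reconcile the removal rules, because the narrative removes the drain only when output has stopped.

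Several parts of the defence stand:
- The removal conflict at low output is partly one of sequence: the narrative also ends in removal, but later.
- The patients affected by the talc conflict are a narrow group.
- The effect on the primary outcome is indirect, because success is itself undefined. If it meant only drainage and talc without admission, the removal mismatch might not change it.

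Some stronger readings are tempting but not supported:
- A reader might infer that the removal rules also clash the other way, for a patient with more than 240 ml/24 h in the bag who is dry when aspirated. That requires the narrative's output to mean only what drains at the visit. The drain is left open to a bag overnight, and the narrative does not say that the bag volume is ignored.
- A reader might infer that a patient who first becomes dry on Day 3 is denied talc, because the Day 3 narrative has no talc step. This is a gap that the table fills by allowing the Day 2 steps to be repeated before talc.
- The different day numbers for talc and removal are not in themselves a contradiction, since the table lets a patient who is dry on Day 2 move straight to the Day 3 steps.

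**Conclusion.** The point holds. The narrative and the table in Section 4 give opposite instructions on talc for a resolved effusion with more than 75% but incomplete expansion because of underlying disease. They also differ on drain removal when output is above 0 and up to 240 ml/24 h, and when the effusion persists on x-ray at 240 ml/24 h or less. The lidocaine doses match only at 66.7 kg. These are conflicting bedside instructions in the protocol itself, so a statistical analysis plan could not settle them.

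The conclusion rests on reading the words as written and the table columns in order. It does not show that any given number of the 10 patients will be affected. Nor would resolving it define success, although any definition needs a single pathway to refer to. It should be fixed.

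**What to change.** Replace the two descriptions with one staged pathway, its thresholds confirmed by the clinical lead:

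- **Talc.** One x-ray expansion criterion. By default use the table's more than 75% apposition, with drain removal without talc at 75% or less because of underlying disease.
- **Drain removal after talc.** One rule that gives the output threshold, defines significant output to match, and says whether an x-ray showing resolution is required before the drain comes out.
- **Lidocaine.** One dose, either fixed or per kg.
- **Timing.** Tie talc to the stage (drain until dry, then x-ray, then talc if the criterion is met) and not to a calendar day.
- **Reference.** State that the primary outcome and deviation reporting refer to this pathway.

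The cost is a protocol wording amendment. It needs no extra patients, and no visits or procedures beyond those that Section 4 already describes in one version or the other.

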6. STUDY PROCEDURES

Study protocol outlined above. Additionally, we will collect Patient related outcome measures relating to breathlessness and pain each day and at day +30. We will also seek patient feedback on the protocol at this point.

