8. DATA MANAGEMENT AND CONFIDENTIALITY

Investigators are required to maintain on file the accurate, complete, and current records relating to this Study. Data will be stored securely in a locked office in a trial file. Digital information will be stored on an NHS computer in a locked office. Only authorized personnel and their designees will have access to these confidential files.

PROTOCOL DEVIATIONS

Protocol deviations should be reported to the sponsor and Chief Investigator using the provided reporting form. The Sponsor and Chief Investigator should then review the details

Feasibility of ambulatory pleurodesis
Protocol V2
IRAS: 330188
CI: [name]
26/06/2023

to assess the impact on the research dataset and also to assess if there are learning points to help prevent a repeat deviation.

MISSING DATA AND DATA QUERIES

Missing data will be included in the analysis. The trials team, CI or an appropriate designee will address any emergent data queries.

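### Protocol Section 4 gives the lidocaine for talc instillation as a fixed 200 mg in the narrative and as 3 mg/kg in the table, and nothing says which governs

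*Protocol*

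**What the plan says.** Protocol Section 4 describes the pathway twice, first as a day-by-day narrative and then as a table with a column for each day.

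- **Narrative, Day 2.** Once drainage has stopped and the chest x-ray is satisfactory, the team is to "proceed to talc slurry instillation (with 20mls 1% lidocaine as per standard practice) and clamp the drain for 2 hours".
- **Table, Day 3 column.** After the x-ray check, the entry reads "Instil 4g steritalic with 3mg/kg Lidocaine and 50ml 0.9% NaCL flush". The next row is a 2-hour clamp.
- **Table, Day 2 column.** For a patient whose drain has stopped producing fluid, it says "Proceed to D3 if no out put".

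Section 6 (Study Procedures) adds no detail on the instillation. It refers back with "Study protocol outlined above". Section 8 requires that "Protocol deviations should be reported to the sponsor and Chief Investigator using the provided reporting form". The primary outcome in Section 3 is "Success delivery of study protocol".

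**The concern.** The narrative and the table describe one act: talc given with lidocaine, then a 2-hour clamp. One fixes the lidocaine amount for everyone and the other scales it to body weight. In general the two cannot both be followed.

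This is a contradictory drug-dose instruction, so what a patient receives may depend on which half of Section 4 the operator reads. It also blurs deviation reporting. Away from one particular weight, a dose that complies with one text departs from the other, and the protocol does not say which of them is the reference.

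**Working it through.** **Inputs**

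- Narrative dose: 20 ml of 1% lidocaine (Section 4, Day 2 narrative).
- Table dose: 3 mg/kg (Section 4, table, Day 3 column). No concentration, volume or cap is given.
- Unit convention: 1% is 1 g per 100 ml, or 10 mg/ml.
- Body weight W: not given anywhere in the protocol. The weights below are assumptions.

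**Step 1. Put both doses in milligrams.**

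Narrative: 20 ml x 10 mg/ml = 200 mg, whatever the weight.

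Table: 3 x W mg.

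**Step 2. Find where they agree.**

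3 x W = 200 gives W = 200/3 = 66.7 kg. This is the only such weight.

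**Step 3. Size of the gap elsewhere.** The difference relative to the narrative dose is (3W - 200)/200.

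| Assumed weight (kg) | Table dose (mg) | Narrative dose (mg) | Table relative to narrative | Narrative dose in mg/kg |
|---|---|---|---|---|
| 40 | 120 | 200 | -40% | 5.0 |
| 50 | 150 | 200 | -25% | 4.0 |
| 60 | 180 | 200 | -10% | 3.3 |
| 70 | 210 | 200 | +5% | 2.9 |
| 80 | 240 | 200 | +20% | 2.5 |
| 90 | 270 | 200 | +35% | 2.2 |
| 100 | 300 | 200 | +50% | 2.0 |

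Each 10 kg moves the table dose by 30 mg, which is 30/200 = 15% of the fixed dose.

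**Step 4. Range of near agreement.**

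- Within 10% (180 to 220 mg): 180/3 = 60 kg to 220/3 = 73.3 kg.
- Within 25% (150 to 250 mg): 150/3 = 50 kg to 250/3 = 83.3 kg.

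**Step 5. Can the two texts be read together?**

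- *As a dose and a ceiling.* The table does not present 3 mg/kg as a maximum, although it uses explicit upper-limit wording for drainage volumes. Even if it were a ceiling, the fixed 200 mg would exceed it in anyone under 66.7 kg.
- *As a full text and its summary.* The table does not simply condense the narrative. It also differs on the day of talc (Day 3 column against Day 2) and on the lung-expansion criterion (more than 75% pleural apposition against full inflation).
- *As an overview with the detail elsewhere.* Section 6 points back to Section 4, so no further text settles the matter.
- *As two different situations.* Take a patient with no output on Day 2. The narrative leads to x-ray and then talc with 200 mg. The table sends the same patient to the Day 3 column, and so to talc with 3 mg/kg.

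**The case against.** The contradiction and the arithmetic are not open to serious challenge. The objections concern how far the point reaches.

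1. **Timing.** The table's instruction to go on to D3 may mean carrying out the Day 3 column at once, or waiting until the next day. On the second reading, the two texts give talc to that patient on different days. This is fair, but the conflict survives: on either reading one patient has one talc instillation with two prescribed lidocaine amounts.

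2. **Deviations.** Section 8 does not define a deviation or say how exact a dose must be, and a difference of a few milligrams near 66.7 kg need not be treated like a large one. This stands as a caution. The protocol still does not say which text a dose should be compared with.

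3. **Assumed weights.** The figures of 40% below and 50% above come from the ends of an assumed range, and between 50 and 83.3 kg the gap is at most 25%. This also stands. The size depends on who is enrolled; the existence of the conflict does not.

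4. **Effect on the trial's conclusion.** Lidocaine accompanies the talc, and nothing in the protocol makes success depend on its dose. With 10 patients and thematic analysis of feedback, no change in the feasibility conclusion has been shown. This is correct, and the point does not rest on such a change.

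**Conclusion.** The concern holds. Section 4 of the current protocol prescribes the lidocaine for talc instillation in two incompatible ways, 200 mg fixed and 3 mg/kg, and nothing says which governs. They coincide only at 66.7 kg. Under the assumed range of 40 to 100 kg, the weight-based dose lies between 80 mg below and 100 mg above the fixed one. The only outside assumption is that range of weights.

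The point must be fixed because it is a contradictory drug-dose instruction in an interventional study, not because of any demonstrated effect on the outcome or its analysis.

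**What to change.** Reconcile the Day 2 narrative bullet and the Day 3 table cell in Section 4. The sponsor's clinical lead should decide on one dose expression, and the protocol should then state it identically, in the same units, in both places. Which expression is right is a clinical decision on which this review takes no position.

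The same amendment can bring the other mismatches between narrative and table into line, notably the day of talc instillation and the lung-expansion criterion.

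The cost is a short protocol amendment that changes one bullet, one table cell, or both. It needs no extra patients, visits or data.

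### Section 4 describes the talc-day procedure twice; the narrative and the table differ on who gets talc, the lidocaine dose and the steps after talc, and nothing says which governs

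*Protocol*

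**What the plan says.** Protocol Section 4 (Overview of study pathway) describes the procedure in a day-by-day narrative and then in a four-column table.

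**Narrative, Day 2.** Once there is no further output, an x-ray must show that the effusion has gone and the lung is fully inflated. If so, the patient has "talc slurry instillation (with 20mls 1% lidocaine as per standard practice) and clamp the drain for 2 hours". Then: "After this we would open the drain again and drain up to 500mls and close the drain for an hour". Then: "We would repeat this as required and again the patient would return home with an ambulatory bag left open". If the effusion has resolved but underlying disease keeps the lung from expanding fully, the drain is taken out and no talc is given.

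**Table, Day 3 column.** Output is assessed, with the entry "Repeat Day 2 protocol if required". An x-ray must then confirm more than 75% pleural apposition. The remaining entries are "Instil 4g steritalic with 3mg/kg Lidocaine and 50ml 0.9% NaCL flush", "Clamp for 2 hour" and "Connect to ambulatory bag and leave 'open'".

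Section 6 refers back to the pathway without ranking narrative over table. The primary outcome in Section 3 is successful delivery of the protocol. Section 8 requires deviations to be reported to the sponsor and the Chief Investigator.

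**The concern.** The trial asks whether this pathway can be delivered, so the pathway is both the intervention and the yardstick. If it is written in two ways, staff can follow one and depart from the other.

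Two of the differences are rules that in general cannot both be obeyed: the x-ray rule decides who receives talc, and the lidocaine rule decides the dose. A third, the drainage step after talc, can make the same care compliant with the table and a deviation from the narrative. The fourth, the flush, is a detail that one version leaves out. None of this is detail normally left to a statistical analysis plan.

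**Working it through.** The plan states no figure to reproduce. All inputs come from Protocol Section 4, set side by side:

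| Item | Narrative (Day 2) | Table (Day 3 column) | Can both be followed? |
|---|---|---|---|
| X-ray rule for talc | Lung fully inflated; otherwise drain removed (underlying disease) | Apposition >75% | Not between 75% and full |
| Lidocaine | 20 ml of 1% | 3 mg/kg | Only at one body weight |
| After the 2-hour clamp | At least one drainage of up to 500 ml and a 1-hour closure, then open bag | Open bag | Narrative care need not breach the table; table care departs from the narrative |
| Flush with talc | Not mentioned | 50 ml saline | Yes, as an addition |

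**1. X-ray rule.** The versions disagree for any apposition above 75% and short of full. Take 80%, with the effusion resolved and underlying disease as the cause. The table gives talc, since 80 > 75. The narrative removes the drain. The Protocol does not say how many of the 10 patients would fall in this band.

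**2. Lidocaine.** A 1% solution is 10 mg/ml, so the narrative dose is 20 × 10 = 200 mg. At weight W kg the table dose is 3W mg. They are equal when 3W = 200, so W = 200/3 = 66.7 kg. The Protocol gives no weights; for illustration, assuming 50 and 80 kg:
- 50 kg: table 3 × 50 = 150 mg; the fixed dose is 200/50 = 4.0 mg/kg, above the table's rule.
- 80 kg: table 3 × 80 = 240 mg; the fixed dose is 200/80 = 2.5 mg/kg, below it.

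**3. Steps after talc.** Thoracocentesis rows in the table: Day 1, 2; Day 2, 2; Day 3, 0. Capped drainages between the 2-hour clamp and going home are therefore at least 1 in the narrative and 0 in the table. The Day 3 instruction to repeat the Day 2 protocol does not supply the step, because it belongs to the output assessment before the x-ray and talc.

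Closed-drain time as written is at least 2 + 1 = 3 h in the narrative and 2 h in the table. That extra hour is uncertain. The Day 1 narrative says "We would then open the drain again and drain up to 500mls before again clamping for one hour", yet the table shows one 1-hour clamp row for two thoracocentesis rows on Day 1, and the same on Day 2. The table thus abbreviates clamps elsewhere. The difference is 0 h if the Day 3 closure is merely abbreviated and at least 1 h if it is not.

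**4. Day of talc.** The narrative places talc on Day 2 and the table on Day 3, but the table's Day 2 column moves a patient with no output straight to the Day 3 steps. The difference therefore applies only to patients who still have output on Day 2.

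**The case against.** The best defence is that Section 4 is an overview and the table condenses the narrative. It also drops the underwater seal bottle and the drain removal for a lung that does not expand. Nothing in the table forbids draining before the bag is connected. On this view the post-talc step is an omission and not an opposing instruction.

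Much of that stands for the post-talc step. Talc follows an output check, so the chest should be nearly dry; the 500 ml figure is a ceiling with no minimum; and both versions end with an open bag and the patient at home. What remains is that the table spells out drainage on Days 1 and 2 and not after talc, while the narrative's first post-talc drainage is unconditional (only its repetition is as required). The table is also not simply subordinate: it alone gives the talc dose, the flush and the apposition threshold.

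The defence does not reach the x-ray rule or lidocaine, where the values conflict. One could suppose that above 75% apposition is what the narrative means by full inflation, but the Protocol does not say so.

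Stronger readings are tempting. A reader might infer that the post-talc difference shifts the primary outcome, since one of 10 patients is 1/10 = 10 percentage points. The documents do not support this: delivery is not defined step by step, and both sequences send the patient home the same day. Nor do they support a claim that only the table allows uncapped drainage at home, because the open bag has no stated limit in either, or that every patient gets talc on a different day.

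**Conclusion.** The inconsistency is real and can be checked on the page. The parts with consequence are the x-ray rule, which changes who receives talc between 75% and full apposition, and the lidocaine rule, which gives different doses at every weight except 66.7 kg, with the fixed dose exceeding 3 mg/kg in lighter patients. The 80% example assumes that underlying disease explains the incomplete expansion; how many patients either difference would affect is unknown.

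The post-talc step is minor: at least one capped drainage against none, and 0 h or at least 1 h of extra closure. Its main consequence is unclear deviation reporting. The flush is a smaller omission, and the day-of-talc difference is partial.

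**What to change.** Issue one reconciled sequence for the talc day, in narrative and table alike, with:
- a single apposition threshold that decides between talc and drain removal;
- a single lidocaine rule, fixed or by weight;
- the flush stated in both places or in neither;
- the post-talc step either added to the Day 3 column after the 2-hour clamp (thoracocentesis of at most 500 ml or to tolerance, 1-hour clamp, repeated as needed) or deleted from the narrative;
- the same day of talc in both for patients who still have output on Day 2.

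Add a sentence saying that delivery and deviations are judged against this sequence. The cost is protocol wording and a clinical choice for each item, with no added visits or patients.

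### Patients' views of the pathway are sought only at day 30, so anyone who dies before then is never asked

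*Protocol*

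**What the plan says.** Section 4 (Overview of study pathway) asks patients to complete "a very brief questionnaire (visual analogue scale) on breathlessness and chest pain". It is given three times on day 1 (before the intervention, one hour after drain insertion and at the end of the day), and then "on day 2 and 3 on first encounter and at the end of the day". Satisfaction enters once, at the end of that paragraph: "We would also repeat the questionnaire on day 30 along with their satisfaction with the protocol".

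Section 6 (Study procedures) repeats the arrangement. Symptom measures are taken daily and at day +30, and then: "We will also seek patient feedback on the protocol at this point". The last time named before that sentence is day +30, which matches section 4.

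The drain comes out on one of three days, depending on where one reads in section 4:

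- On day 2, if the effusion has resolved but the lung has not expanded: "then we would simply remove the chest drain as pleurodesis will not be possible".
- On day 3 in the text, after which: "We would then consider the intervention complete and revert to standard care".
- On day 4 in the table: "Seldinger drain removed".

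The use to be made of the views is stated in section 2 (Background): the team will "collect patient feedback to see if our patients consider it an acceptable and worthwhile intervention". Patient perspectives are the only secondary objective (sections 1 and 3), and a thematic analysis of the feedback is the one analysis the protocol names (Statistical analysis plan, under Sample size).

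**The concern.** Section 2 describes these patients as often having a heavy symptom burden and not long to live. Under the schedule as written, a patient who completes the pathway and dies before day 30 is never asked what they thought of it. A patient who deteriorates may or may not be able to answer when the call comes.

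The judgement on acceptability would then come only from those alive and well enough to respond about four weeks later. Patients who die early may answer differently on whether the time and procedures were worth it. Which way the difference would run cannot be said from the documents.

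This is not a matter that an analysis plan can settle. The protocol fixes when the question is asked, and section 8's statement that missing data will be included in the analysis cannot supply answers that were never requested.

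**Working it through.** The protocol states no figure on this point, so there is none to reproduce. The check has three parts.

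**1. What is asked, and when (section 4).** Questionnaires before day 30: 3 on day 1 + 2 on day 2 + 2 on day 3 = 7, all on symptoms only. Day 30 is the eighth and the only one that asks about the pathway. If the drain is removed on day 2, the day 3 pair may not take place, which leaves 3 + 2 = 5 before day 30. None of these asks about the pathway either.

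**2. Gap from drain removal to the question.**

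- Day 2 removal (lung not expanded): 30 − 2 = 28 days.
- Day 3 removal (text): 30 − 3 = 27 days.
- Day 4 removal (table): 30 − 4 = 26 days.

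The gap is shorter if drainage is prolonged. The day 3 and day 4 versions are a separate inconsistency that must be reconciled; the point here holds under either.

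**3. Illustrative size.** The sample size is n = 10 (protocol, Sample size). The loss by day 30, p, is **assumed** at 5% to 30%.

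- Expected number unheard = 10p.
- Chance of at least one = 1 − (1 − p)^10. For example, at p = 0.10: 1 − 0.9^10 = 0.651.

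To see what an additional question at drain removal would save, suppose further that all loss is by death at a constant rate from day 1 to day 30:

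- h = −ln(1 − p)/29, with implied median survival ln 2/h.
- Expected number lost before a day 3 removal = 10(1 − e^(−2h)).
- Expected number lost before a day 4 removal = 10(1 − e^(−3h)).

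For example, at p = 0.20: h = 0.2231/29 = 0.00769 per day; median = 0.693/0.00769 = 90 days; lost by day 3 = 10(1 − e^(−0.0154)) = 0.153.

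| Assumed loss by day 30 | 5% | 10% | 20% | 30% |
|---|---|---|---|---|
| Expected number unheard of 10, as planned | 0.5 | 1 | 2 | 3 |
| Chance of at least one unheard | 40% | 65% | 89% | 97% |
| Implied median survival (days) | 392 | 191 | 90 | 56 |
| Expected number never asked, if also asked at removal on day 3 | 0.035 | 0.072 | 0.153 | 0.243 |
| Expected number never asked, if also asked at removal on day 4 | 0.053 | 0.108 | 0.228 | 0.362 |

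The share of the loss avoided is 92–93% for day 3 (at 30%: 1 − 0.243/3 = 92%) and 88–89% for day 4 (at 30%: 1 − 0.362/3 = 88%).

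**The case against.** The strongest reply is that day 30 is a deliberate and sensible choice. It coincides with the length of follow-up and with the definition of the end of the trial in section 1. Whether the treatment was worth having depends on whether fluid and symptoms return, which cannot be known on the day the drain comes out. This stands, and it is a reason to keep day 30. It is not a reason to make day 30 the only time of asking.

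A second reply is that the design already limits the loss. Entry requires predicted survival beyond 30 days (section 5), the day 30 survey can be done by telephone (section 7), and reasons for withdrawal are sought (section 11). Each helps. But the entry limit is a prediction whose threshold coincides with the survey day, the telephone reaches only the living, and withdrawal reasons do not cover death.

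Third, the loss rates are assumptions. This is correct. The upper two rates imply median survival of about 90 and 56 days, which nothing in the protocol confirms for patients selected in this way. At 5% to 10% loss, nine or more of the ten views are still expected. The share avoided is also close to the fraction of the 29 days that follows removal (27/29 = 93%, 26/29 = 90%) whatever the mortality, and it covers deaths only. The figures show the order of size and are not evidence that a given loss will occur.

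Finally, this is a small feasibility study, and a thematic analysis does not need complete response as an estimated proportion would. That limits the seriousness. It does not answer the fact that one group is left out by design.

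**Conclusion.** The point holds. The protocol asks for views of the pathway once, 26 to 28 days after planned drain removal, and makes no provision for hearing from patients who die before then. That conclusion follows from the schedule and the described population and does not depend on any assumed rate.

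Its size does depend on assumption: between half a patient and three patients of ten for losses of 5% to 30%. Under a constant death rate, asking also at removal would avoid roughly nine-tenths of that loss. Symptom scores from patients who die early would still contribute to the secondary outcome, and the primary outcome is untouched. The change should be made because the loss cannot be recovered and touches the sole secondary objective, but it does not threaten the study as a whole.

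**What to change.** Put the satisfaction and feedback questions also at the visit when the drain is removed, whichever day that is and including removal without pleurodesis. Ask them at withdrawal too, if the patient agrees. Keep day 30 as a second time point, since the later course bears on whether the pathway was worthwhile. Report how many patients responded at each time point. Amend sections 4 and 6 so that they say the same.

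The cost is a few minutes at a contact that already takes place and a short change of wording. The drawback is a small added burden for ill patients.
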